9.1 Genotyping

Genotyping will be assessed by any historical records of the disease or new genetic testing for inclusion in the study. Date of the test, and any genetic mutation will appear on subject level listings.

9.2 Baseline Characteristics

A summary listing of baseline characteristics will be produced showing select demographic, ocular history, disease history (including date of diagnosis and age at diagnosis), visual acuity, and other ocular information.

10. Medical History and Concomitant Medications

10.1 Medical History

Medical history will be coded using Medical Dictionary for Regulatory Activities (MedDRA) version 20.0.

Non-ocular medical history will be summarized using discrete summary statistics and presented by dose group at the subject (i.e., counts and percentages based on incidence of subjects with an event) and event level by System Organ Class (SOC) and Preferred Term (PT) using the Safety population. Ocular medical history will be similarly summarized at the subject level (i.e., incidence of subjects with an event) and event level, separately for the treated eye and contralateral eye. If a subject reports the same PT multiple times within the same SOC, that PT will only be reported once within that SOC. As with the PT, if a subject reports multiple conditions within the same SOC, that SOC will only be reported once.

Listings of medical history will be generated separately for ocular and non-ocular data.

10.2 Concomitant Medications

Concomitant medications will be coded using WHO Drug Dictionary (Enhanced B2, March 2017) and summarized to the therapeutic drug class (Anatomical Therapeutic Chemical [ATC] 4 classification) and preferred name. If the ATC 4 classification is not provided, the next lowest classification that is provided in the coding dictionary will be used. The preferred name will be defined as the active ingredient; if the active ingredient is not provided or includes more than two ingredients (e.g., multivitamins) then the drug name will be summarized as the preferred name. Any un-coded terms will be summarized under the ATC classification and preferred name of "Encoded."

Concomitant medications are defined as those medications listed as having been taken 1) prior to initiation of study drug administration and continuing for any period following the first administration of study drug or 2) at any time following the first administration of study drug or 3) any pre-medication taken in conjunction with the normal conduct of the study (e.g., and medications for pupil dilation and/or general sedation/anesthesia for the IVT injection of the study drug).

Non-ocular and ocular concomitant medications will be summarized separately using the Safety population. Medications will be tabulated for each dose group using frequencies and percentages, ocular medications will be further summarized separately for treated eye and contralateral eye. Subjects may have more than 1 medication per ATC text. At each level of subject summarization, a subject will be counted once if he/she reports 1 or more medications. Percentages will be based on the number of subjects in each dose group. Listings of concomitant medications will be generated separately for ocular and non-ocular data.

11. Treatment Exposure

All doses are observed and administered by study staff. Therefore, treatment compliance will not be calculated. Treatment exposure will be assessed by calculating the number of doses expected, number of actual doses received, cumulative dosage (µg), and the duration of exposure. Number of doses expected will be determined by the highest visit completed, as follows:

- Study discontinuation after Visit 2 but before Visit 9 (Month 3) implies 1 dose was expected.
- Study discontinuation after Visit 9 but before Visit 13 (Month 6) implies 2 doses were expected.
- Study discontinuation after Visit 13 but before Visit 18 (Month 9) implies 3 doses were expected.
- Study discontinuation after Visit 18, or completion of study, implies 4 doses were expected.

Number of actual doses received will be summarized as both continuous and categorical outcome (i.e., 1, 2, 3, or 4 doses received). Duration of exposure will be calculated in days as the date of last dose – the date of first dose + 1. Treatment exposure parameters will be summarized descriptively by dose group and cohort.

12. Safety and Tolerability Analyses

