PLR	Pupillary Light Reflex
PP	Per Protocol
PT	Preferred Term
RTF	Rich Text Format
SAE	Serious Adverse Event
SAP	Statistical Analysis Plan
SD	Standard Deviation
SDC	Statistics and Data Corporation, Incorporated
SOC	System Organ Class
$T_{1/2}$	Half-Life
TEAE	Treatment-Emergent Adverse Event
VA	Visual Acuity
V_d	Apparent Volume of Distribution
VEP	Visual Evoked Potential
VFQ-25	25-Item Visual Functioning Questionnaire
WHO DDE	World Health Organization Drug Dictionary Enhanced
WOCBP	Women of Childbearing Potential

1. Introduction

The purpose of this statistical analysis plan (SAP) is to describe the planned analyses and reporting in support of protocol PQ-110-001, version 6.0 dated 02-Aug-2018.

This SAP is being written with due consideration of the recommendations outlined in the most recent International Council for Harmonisation (ICH) E9 Guideline entitled Guidance for Industry: Statistical Principles for Clinical Trials and the most recent ICH E3 Guideline, entitled Guidance for Industry: Structure and Content of Clinical Study Reports.

This SAP describes the data that will be analyzed and the subject characteristics, efficacy, and safety assessments that will be evaluated. This SAP provides details of the specific descriptive statistical methods that will be used.

In addition to this SAP, inferential analyses will be generated by [REDACTED] which will also be used to support the CSR. The descriptions of methods and statistical analyses used for these inferential analyses are described separately within the scope of the Cytel SAP of which a copy has been included in whole in [REDACTED] and which should be read in conjunction with this SAP.

The statistical analysis methods presented in this document will supersede the statistical analysis methods described in the clinical protocol. If additional analyses are required to supplement the planned analyses described in this SAP they may be completed and will be identified in the Clinical Study Report (CSR). Study Objectives

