2.4 Study Visits

Study visits will be referred to in all tables and listings as the planned study day corresponding to the visit to enable reviewers to understand the assessment timing without referring to the protocol visit schedule shown in Table 1. Screening assessments may be repeated at a Re-Screening visit to reevaluate eligibility or safety parameters at the Investigator's discretion. In listings the re-screening visit will be "Unscheduled (Day -28 to -1)" and will only be used for further analyses if an average of all pre-dose measures is used for baseline. Dosing visits can occur over multiple days due to time constraints on subjects' schedules and visit procedures. Note that there is no Day 0 and that Day 1 corresponds to the day of first treatment. Any unscheduled visits outside of _____ will be noted as "Unscheduled" on tables and listings. The following table shows the scheduled visits, their planned study day and the acceptable visit windows for each scheduled visit. Scheduled visits that occur outside of the visit window will not be considered unscheduled visits, but will be presented and summarized as the scheduled visit.

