7.6 Interim Analyses

An interim analysis of all outputs was conducted after the eighth subject in the study had at least 3 months of data in accordance with SAP version 1.0. The interim analysis included all available study data (all monitored and cleaned) at the time of the data snapshot, .

An additional interim analysis (interim analysis 2) of all outputs was performed using all available data (all monitored and cleaned) from all 11 subjects at the time of the data snapshot (ie, after mid-August 2018). SAP Version 1.0 was in effect at the time of this interim analysis.

A third interim analysis, consisting of all outputs produced for interim analysis #2, will be performed once the last subject has completed Visit 15 (end of study visit) and there is a soft lock. This third interim analysis (planned for August 2019) will consist of all outputs for interim analysis 2 and will include all available study data (all monitored and cleaned) at the time of the data snapshot.

No alpha or family-wise error rate adjustments are made for interim analyses at the data for this early phase 1b/2 trial as all analyses are exploratory.

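### The SAP's visit numbers for Month 3, Month 9 and end of study disagree with the supplied protocol and with each other (SAP 11 and 7.6)

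*SAP*

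**What the plan says.** SAP section 11 (Treatment Exposure) sets the derivation: "Number of doses expected will be determined by the highest visit completed". The first boundary is "Study discontinuation after Visit 2 but before Visit 9 (Month 3) implies 1 dose was expected". The second interval runs from Visit 9 to Visit 13, labelled Month 6. The third is "Study discontinuation after Visit 13 but before Visit 18 (Month 9) implies 3 doses were expected", and the last is "Study discontinuation after Visit 18, or completion of study, implies 4 doses were expected".

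SAP section 7.6 says that the third interim analysis "will be performed once the last subject has completed Visit 15 (end of study visit) and there is a soft lock".

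The protocol numbers the same visits in four places, and they agree:
- Section 7.3 puts dosing at Visit 2 (Day 1), Visit 8 (Month 3), Visit 13 (Month 6) and Visit 17 (Month 9).
- Section 4.2.2.1 has subjects who stop study drug attend whichever of Visits 8, 13, 17 and 21 remain.
- Sections 7.4 and 13.6 make Visit 21 the end of study visit.

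The SAP introduction says the plan supports "protocol PQ-110-001, version 6.0 dated 02-Aug-2018".

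**The concern.** The visit numbers are not background description. Those in section 11 are the cut-points of a derived variable, and the one in section 7.6 sits in the trigger for an analysis. Three of them differ from the protocol (9 for 8, 18 for 17, 15 for 21), and two of them, 15 and 18, cannot both be right within the SAP. A programmer who codes section 11 by number would assign fewer doses expected than the protocol schedules for a subject whose last completed visit is the second or fourth dosing visit. The exposure table could then show a subject with more doses than were expected. No safety, efficacy or primary-endpoint result depends on this variable.

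**Working it through.** **Step 1: reproduce the protocol's numbering.** The inputs are Day 1 = Visit 2 (protocol 7.3), Screening = Visit 1 (assumed), and the follow-up pattern in protocol 4.2.1.3. After each dose there is a next-day visit, a 7-day visit, a 14-day telephone visit (dose 1 only), a 1-month visit, a 2-month visit (doses 1 and 2 only) and a 3-month visit. Counting in order gives:

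| Dose | Dosing visit | Next day | 7 days | 14-day call | 1 month | 2 months | 3 months |
|---|---|---|---|---|---|---|---|
| 1 | 2 | 3 | 4 | 5 | 6 | 7 | 8 |
| 2 | 8 | 9 | 10 | – | 11 | 12 | 13 |
| 3 | 13 | 14 | 15 | – | 16 | – | 17 |
| 4 | 17 | 18 | 19 | – | 20 | – | 21 |

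This reproduces the protocol's 8, 13, 17 and 21. In this numbering, the SAP's Visits 9 and 18 are the days after doses 2 and 4, and Visit 15 is the 7-day visit after dose 3.

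**Step 2: compare the two sets.**

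| Time point | Protocol | SAP |
|---|---|---|
| Month 3 | 8 | 9 |
| Month 6 | 13 | 13 |
| Month 9 | 17 | 18 |
| Month 12 / end of study | 21 | 15 |

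**Step 3: could a different numbering base explain it?** A uniform shift cannot, because Month 6 stays at 13 while Months 3 and 9 each move by one. The gaps between successive dosing visits show the same thing:
- Protocol: 8 − 2 = 6, 13 − 8 = 5, 17 − 13 = 4.
- SAP 11: 9 − 2 = 7, 13 − 9 = 4, 18 − 13 = 5.

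There is a 2-month visit after dose 2 but not after dose 3, so the gap from dose 2 to dose 3 should be one longer than the gap from dose 3 to dose 4. SAP 11 has it one shorter.

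**Step 4: check the SAP against itself.** Month 9 is Visit 18 in section 11 and end of study is Visit 15 in section 7.6. In any ascending numbering, end of study follows Month 9, so its number must exceed 18. This step does not use the protocol.

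**Step 5: apply the rule.** Doses expected = 1 + the number of later boundaries at or below the highest completed visit. Doses scheduled = the number of protocol dosing visits (2, 8, 13, 17) at or below it. For Visits 2 to 21 (20 values):

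| Highest completed visit | Scheduled | Expected, boundaries 9, 13, 18 | Expected, boundaries 8, 13, 17 |
|---|---|---|---|
| 2–7 | 1 | 1 | 1 |
| 8 | 2 | **1** | 2 |
| 9–12 | 2 | 2 | 2 |
| 13–16 | 3 | 3 | 3 |
| 17 | 4 | **3** | 4 |
| 18–21 | 4 | 4 | 4 |

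The SAP boundaries disagree with the schedule at 2 of the 20 visit numbers, each time by one dose. The protocol boundaries disagree at none. These are counts of visit numbers, not of subjects.

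**The case against.** The best defence is that the intent is plain. Each boundary in section 11 carries its month, section 7.6 names the visit in words, and for reporting "Study visits will be referred to in all tables and listings as the planned study day corresponding to the visit". A careful programmer would probably code the rule correctly. That stands, and it is why the point is minor. It does not make the numbers right.

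The second defence is that Step 5 applies SAP boundaries to protocol visit numbers. The visit table in SAP 2.5 is not in the supplied text. If it numbers Month 3 as Visit 9 and Month 9 as Visit 18, section 11 has no mismatch in its own terms. SAP 15.2 adds weight to this: it describes a protocol baseline rule based on the highest visual function, whereas the supplied protocol averages repeat measures, so some SAP text may have been written against another protocol version. This stands as a reason to check before editing. It cannot reconcile Visit 15 with Visit 18, and SAP 17.1 gives alignment with version 6.0 as a reason for the revision.

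Four stronger readings might be inferred, and the documents do not support them:
- *The third interim analysis would run after dose 3.* Section 7.6 labels the visit as end of study, requires a soft lock and plans the analysis for August 2019, about a year after the mid-August 2018 snapshot that already held all 11 subjects.
- *The rule yields more doses received than expected.* The comparison is with doses scheduled. Subjects who stop study drug still attend later dosing-time visits, and doses can be held or skipped, so the excess is possible but not implied.
- *A subject who stops at a boundary visit gets no value.* The lead-in classifies by highest visit completed, which assigns that subject.
- *Early withdrawers would all be given four expected doses, because protocol 7.4 asks for end-of-study assessments at withdrawal.* No document says these are recorded as Visit 21, and the rule turns on when discontinuation occurred.

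**Conclusion.** The point holds as a minor inconsistency that should be corrected. The conflict between Visits 15 and 18 is certain from the SAP alone. The differences from the protocol (9 against 8, 18 against 17, 15 against 21) hold for the protocol text supplied. The documents do not allow a check that this text is version 6.0.

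The size is an under-count of one scheduled dose at highest completed visits 8 and 17, assuming visits are recorded in protocol numbering with Screening as Visit 1. Only the descriptive doses-expected row is exposed. Doses received, cumulative dose, adverse events and the primary endpoint do not change. The documents do not show that any subject's last completed visit was 8 or 17.

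**What to change.** First check the numbers against the protocol version 6.0 schedule and the SAP 2.5 visit table. If they confirm the protocol's numbering:

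- **SAP 11:** replace Visit 9 with Visit 8 (Month 3) and Visit 18 with Visit 17 (Month 9), and state the intervals inclusively. At or after Visit 2 but before Visit 8: 1 dose expected. At or after Visit 8 but before Visit 13: 2. At or after Visit 13 but before Visit 17: 3. At or after Visit 17, or completion of study: 4.
- **SAP 7.6:** replace Visit 15 with Visit 21 (Month 12/EOS).

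Alternatively, key both passages to Months 3, 6, 9 and 12 and drop the visit numbers, which removes the dependence on any numbering.

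The cost is a few words in the SAP and a check of one derived variable. It needs no new data and no change to trial conduct.

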12.1 Adverse Events

An Adverse Event (AE) is defined as any untoward medical occurrence associated with the use of a drug in humans, whether or not the event is considered drug-related. An AE can therefore be any unfavorable, noxious and unintended sign (e.g., an abnormal laboratory finding), symptom, or disease temporally associated with use of a study drug or other protocol-imposed intervention, regardless of attribution. Any pre-existing medical condition that worsens after first administration of the study drug will also be considered a new AE. The AE reporting period ends 90 days following the last administration of study drug or the subject's EOS visit, whichever is later. Adverse events and SAEs related to study drug that persist >90 days after the last study drug dose should be followed until resolution or until they return to baseline, stabilize, the subject is lost to follow-up, or it has been determined that the study drug or participation is not the cause of the AE/SAE. All AEs will be coded using the MedDRA 20.0.

Treatment-emergent adverse events (TEAEs) are defined as any event that occurs or worsens on or after the day that study treatment is initiated. Adverse events recorded in the eCRF which began prior to treatment will not be included in the summary tables but will be included in the AE data listings.

All significant medical conditions including signs/symptoms of the underlying diagnosis found during the screening period and up to initiation of dosing (Visit 2) will be captured as medical history. Any event/condition related to participation in the study or study procedures but not related to underlying or concomitant disease that is noted after Screening up to the date of first dose will be captured as a non-treatment emergent AE (non-TEAE).

An overall summary will be presented that includes the number of TEAEs and the number and percentage of subjects who experienced at least one TEAE, by dose group. This summary will also include breakdowns of TEAEs further categorized as ocular (treated eye and contralateral eye separately) or non-ocular, serious TEAEs (SAEs), TEAEs by maximum severity, TEAEs by maximum relationship, and TEAEs leading to subject withdrawal.

Additional summaries of TEAEs will be provided showing the number and percentage of subjects who experienced at least one TEAE. These summaries will be presented by system organ class (SOC) and preferred term (PT). Non-ocular TEAEs will be summarized using discrete summary statistics and presented by dose group at the subject and event level by SOC and PT. Ocular TEAEs will be similarly summarized at the subject level for study and contralateral eyes separately. If the same PT is reported for a subject multiple times within the same SOC, that PT will only be reported once within that SOC. As with the PT, if multiple conditions within the same SOC are reported, that SOC will only be reported once. In the summary, SOC will be listed in ascending alphabetical order; PTs will be listed in order of descending frequency for all subjects within each SOC. The occurrence of non-ocular and ocular TEAEs will also be tabulated by SOC and PT for the following: maximal severity and suspected relationship to study drug.

Separate summaries will be provided for the following categories of AEs:

- All AEs
- Ocular TEAEs in the treated eye and contralateral eye (includes treatment-related events)
- Non-ocular TEAEs (includes treatment-related events)
- TEAEs leading to treatment discontinuation
- TEAEs leading to subject withdrawal or treatment discontinuation
- Serious TEAEs (SAEs)
- TEAEs by maximum severity
- TEAEs by maximum relationship
- TEAEs of special Interest

Severity of an AE is defined as a qualitative assessment of the degree of intensity of an AE as determined by the Investigator or reported to him/her by the subject. The assessment of severity is made

irrespective of relationship to study drug or seriousness of the event and should be evaluated according to the following scale:

- *Mild*: Does not interfere with subject's usual function.
- *Moderate*: Interferes to some extent with subject's usual function.
- *Severe*: Interferes significantly with subject's usual function.

Summaries of TEAEs by maximal severity will be presented for ocular AEs and non-ocular AEs separately. The number of subjects with any TEAEs (along with percentages) will be tabulated by SOC and PT within each SOC by dose group. To count the number of subjects with any TEAEs, if a subject has multiple TEAEs coded to the same PT within the same SOC, the subject will be counted once under the maximal severity.

The Investigator will make a causality assessment about the relationship of each AE to study drug. To ensure consistency of AE and SAE causality assessments, the Investigators were instructed to apply the following general guideline:

- *Not Related*: The AE has an etiology other than the study drug (e.g., preexisting medical condition, underlying disease, intercurrent illness, or concomitant medication); and/or the AE has no plausible temporal relationship to administration of the study drug (e.g., cancer diagnosed 2 days after first dose of study drug).
- *Possibly Related*: An AE that follows a reasonable temporal sequence from administration of the study drug, follows a known or expected response pattern to the study drug, but that could readily have been produced by a number of other factors.
- *Probably Related*: An AE that is clearly related to the study drug or its administration (i.e., an event that follows a reasonable temporal sequence from administration of the study intervention, follows a known or expected response pattern to the suspected intervention, that is confirmed by improvement on stopping and reappearance of the event on repeated exposure and that could not be reasonably explained by the known characteristics of the subject's clinical state).
- *Definitely Related*: The AE is clearly related to the study drug; a re-challenge confirms the association (not required or desirable in some circumstances but provides strong evidence when it happens).

For all AEs and SAEs, Investigators will make separate assessments of causality about the relationship of the event to study drug.

All TEAEs will be presented in a subject listing. The TEAEs leading to study treatment discontinuation will be listed separately. In addition, all serious AEs will be presented in a separate listing.

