##### **b. Persistent or Recurrent Adverse Events**

A persistent AE is one that extends continuously, without resolution between subject evaluation time points. Such events should only be recorded once in the eCRF unless their severity increases. If a persistent AE becomes more severe or occurs more frequently, it should be recorded again on the AE eCRF with the increased severity grading.

A recurrent AE is one that occurs and resolves between subject evaluation time points and subsequently recurs. All recurrent AEs should be recorded individually on the AE eCRF.

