1.3 Exploratory Objectives

1.4 Primary Endpoint

- Frequency and severity of ocular AEs in the treated and contralateral eyes

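### Ocular TEAEs, the primary endpoint, have no event count by preferred term, although non-ocular TEAEs do, so no described table shows how often a given ocular term recurred over up to four injections

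*SAP*

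**What the plan says.** SAP 1.4 gives the primary endpoint as "Frequency and severity of ocular AEs in the treated and contralateral eyes". Non-ocular AEs are secondary (SAP 1.5). Neither the protocol nor the SAP says whether frequency means subjects affected or events.

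SAP 12.1 sets the counting rules by term in consecutive sentences:

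- Non-ocular: "Non-ocular TEAEs will be summarized using discrete summary statistics and presented by dose group at the subject and event level by SOC and PT".
- Ocular: "Ocular TEAEs will be similarly summarized at the subject level for study and contralateral eyes separately".
- Repeats: "If the same PT is reported for a subject multiple times within the same SOC, that PT will only be reported once within that SOC".

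The tables by severity likewise count a subject once per term, at the worst grade.

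The same section plans a broader table: "An overall summary will be presented that includes the number of TEAEs and the number and percentage of subjects who experienced at least one TEAE". It is to include "breakdowns of TEAEs further categorized as ocular (treated eye and contralateral eye separately) or non-ocular". All TEAEs also go into a subject listing.

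On data capture, Protocol 9.4.3 b states: "All recurrent AEs should be recorded individually on the AE eCRF". It also has a persistent AE entered again if it becomes more severe or more frequent.

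**The concern.** The primary endpoint has a thinner tabulation by term than the secondary one. That matters somewhat in this design. Protocol 2.4 gives repeat-dose safety as a reason for using four injections, and the causality scale (Protocol 9.3.2, SAP 12.1) treats return of an event on re-exposure as evidence of a drug relationship. A reader of the ocular PT table will want to know whether a term appeared once and settled or came back after each injection. With subject counts alone, both patterns give the same entry.

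**Working it through.** The plan states no event rate, power or alpha for this endpoint, so there is no figure to reproduce. The check compares the texts and then illustrates the size.

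**Step 1: does the word for similarity bring in the event level?** SAP 10.1 describes ocular medical history with the same construction and names both the subject level and the event level, by eye. SAP 12.1 names only the subject level for ocular TEAEs. Where the SAP wants both levels for eye data, it says so. The event level is therefore not clearly specified here, although a drafting slip is possible.

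**Step 2: what do the other outputs show about repeats?**

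| Output | Counts repeats? | Split by ocular PT? |
|---|---|---|
| Ocular SOC/PT table (SAP 12.1) | No | Yes |
| Overall summary, ocular by eye (SAP 12.1) | Yes | No |
| By-visit examination and special-interest outputs (SAP 12.2.1, 12.3, 12.4, 14.6, 14.7) | In part: show timing by visit | Only for the findings covered |
| TEAE listing (SAP 12.1) | Yes | Yes, but counted by hand |

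No row is a table that counts repeats by ocular PT. The special-interest flags mark examinations dated between onset and resolution, so one long event and two short ones can look alike.

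**Step 3: what the overall total cannot resolve.** Take 11 subjects (SAP 7.6), four injections each (the planned maximum, SAP 2.1) and, as an assumption, at most one event of a term per injection. Suppose two ocular PTs both appear as 11/11 and the overall ocular total is 55.

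- PT A after every injection, PT B once per subject: 11 × 4 + 11 × 1 = 44 + 11 = 55.
- The reverse: 11 × 1 + 11 × 4 = 11 + 44 = 55.

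The subject counts and the total are identical, yet a different term recurs. This is an extreme constructed case, not a forecast.

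**Step 4: likely size.** Let p be the chance of a given term after one injection. The documents give no p, so 0.05 to 0.75 is an assumed range, with independent injections.

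- Expected subjects affected = 11 × [1 − (1 − p)^4]
- Expected events = 11 × 4 × p
- Share of events beyond each subject's first = 1 − subjects/events

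| p | Subjects | Events | Share beyond first |
|---|---|---|---|
| 0.05 | 2.04 | 2.2 | 7% |
| 0.10 | 3.78 | 4.4 | 14% |
| 0.25 | 7.52 | 11.0 | 32% |
| 0.50 | 10.31 | 22.0 | 53% |
| 0.75 | 10.96 | 33.0 | 67% |

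For example, at p = 0.25: 1 − 0.75^4 = 0.684; 11 × 0.684 = 7.52; 11 × 4 × 0.25 = 11.0; 1 − 7.52/11.0 = 0.32. The two counts nearly agree for uncommon terms and separate only when a term follows a sizeable share of injections.

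**The case against.** The strongest reply is that little is missing.

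- **Repeats are counted.** A reader might infer that the primary endpoint loses recurrence altogether. The documents do not support this. The overall summary gives ocular TEAE numbers per eye, each recurrence is its own record, all are listed, and Protocol 8.12 provides narratives for every subject. With 11 subjects, the listing can be read directly.
- **Inflammation is followed by visit.** Flare grade and the posterior segment examination, which includes vitreous haze, are summarized at each visit, and special-interest counts by visit are planned for IOP, SD-OCT and NIRAF. For these findings, timing across doses is largely visible in tables.
- **Subject counts follow the protocol.** Protocol 10.6.1 reports numbers and percentages of subjects and keeps the most severe of repeated events. A subject incidence is a correct quantity. A reader might infer that frequency is understated fourfold, but subject and event counts measure different things, and that multiple needs every affected subject to have the term exactly once after each of four injections.
- **The text is not clean.** The once-per-term rule is not confined to ocular events, so it also sits awkwardly with the non-ocular event counts. Parts of the SAP are not visible, and table shells might show an ocular event column.

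The first three replies stand and limit the point to a missing column by term. The fourth supports clarifying the text: the wording as it reads does not specify that column, whatever the shells contain.

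**Conclusion.** The point holds in narrow form and is minor. SAP 12.1 specifies ocular TEAEs by SOC and PT at subject level only, while the secondary non-ocular TEAEs also get event counts. How often a specific ocular term recurred can be worked out from the listing, partly from by-visit outputs for certain findings, and only in aggregate from the overall summary.

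No data are lost, and this descriptive study's validity is not threatened. The size depends on an event rate that the documents do not give: under the assumptions above, between 7% and 67% of a term's events would fall outside the subject count, with the low end applying to uncommon events. The conclusion rests on the visible SAP text. If the table shells already carry an ocular event column, only the wording needs to catch up.

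**What to change.** Amend SAP 12.1 as follows:

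1. Specify that ocular TEAEs are tabulated by SOC and PT with both the number of subjects and the number of events, by dose group, separately for the treated and the contralateral eye. State that frequency in the primary endpoint covers both counts.
2. Confine the once-per-PT and once-per-SOC rule to the subject counts, for ocular and non-ocular tables alike.
3. Count a persistent AE that is entered again because it worsened separately from a true recurrence. Otherwise the event column mixes the two.
4. For the treated eye, show events by the most recent injection (first to fourth), with the number of injections given at that step as the denominator. A single ratio of all events to all injections would not separate early from late events. Events whose start date does not allow assignment go in their own row.

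The cost is a few lines of SAP text, one added column and one small table. The individually recorded AEs and the dosing records already supply the data (SAP 11 summarizes doses received), so nothing changes in data collection or in the conduct of the study.
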